6.2 Preparation, Handling, Storage, and Accountability

The investigator or designee must confirm study interventions have been received and, if a temperature data logger has been included, appropriate temperature conditions have been maintained during transit. Any discrepancies are reported and resolved before use of the study intervention.

Only participants randomized in the study may receive study intervention and only authorized site staff may supply, prepare or administer study intervention. All study intervention must be stored in a secure, environmentally controlled, and monitored (manual or automated) area in accordance with the labeled storage conditions with access limited to the investigator and authorized site staff.

The investigator or the head of the medical institution (where applicable) is responsible for study intervention accountability, reconciliation, and record maintenance (i.e., receipt, reconciliation, and final disposition records). Drug returns, reconciliation and destruction information will be captured in the IRT.

A record of the number of tablets dispensed to and taken by each participant must be maintained and reconciled with study treatment and compliance records. An adequate record of receipt, distribution, and return/destruction of all study treatment must be captured on the dispensing log and/or in the IRT.

Study drug tablets not returned will be considered to have been taken unless otherwise specified. At the end of the study, any remaining drugs will be collected and returned to the sponsor, destruction depot or destroyed at the site. Any discrepancies between the returned and expected returned study drugs should be explained.

Study intervention will be dispensed at the study visits summarized in SoA (see Section 1.3). Returned study intervention should not be re-dispensed to the participants.

6.3 Assignment to Study Intervention

Eligible participants who meet all the inclusion criteria and none of the exclusion criteria will be assigned a randomization number and randomly allocated in a 2:1 ratio to receive either zabedosertib or matching placebo.

The randomization will be done in blocks.

6.4 Blinding

As this is a double-blind study design, both investigators and participants will be blinded to study interventions.

All participants will be centrally assigned to randomized study intervention using Interactive Response Technology (IRT); the use of central randomization via IRT will minimize potential bias. Before the study is initiated, the directions for the IRT will be provided to each site.

The IRT will be programmed with blind-breaking instructions. In case of an emergency, the investigator has the responsibility for determining if unblinding of a participant's intervention assignment is warranted. If the investigator is unavailable, and a treating physician not associated with the study requests emergency unblinding, the emergency unblinding requests are forwarded to the study specific emergency medical advice 24 hours / 7 days service. Participant safety must always be the first consideration in making such a determination. If

the investigator decides that unblinding is warranted, the investigator should make every effort to contact the sponsor prior to unblinding a participant's intervention assignment unless this could delay emergency treatment of the participant. If a participant's intervention assignment is unblinded, the sponsor must be notified within 24 hours after breaking the blind. The date and reason that the blind was broken must be recorded in the source documentation and case report form, as applicable. In order to maintain the blind, study interventions will be packaged in bottles labeled with a unique number which will be pre-printed on each bottle.

Bioanalytical staff will be unblinded according to the corresponding Bayer standard operating procedure (SOP). Pharmacometrics and pharmacokinetics staff may also be unblinded according to Bayer SOPs. PK and exposure-response analysis might be performed using population approaches (popPK and popPK/PD, e.g. by non-linear mixed effect modeling). Analysis and report will be done under a separate cover if applicable. This evaluation might be started prior to database lock. If this is applicable, appropriate measures will be taken to maintain blinding of the study team, e.g. data will be stored separately, and members of the study team will neither have access to the randomization list nor to individual data.

6.5 Study Intervention Compliance

Participants will be requested to bring along all used and unused study intervention including packaging material to selected visit (see SoA, Section 1.3). Any discrepancies between actual and expected amount of returned study intervention or any discrepancies with the patient drug intake diary must be discussed with the participant at the time of the visit and should be resolved, if possible.

The data of participant's daily intake of study intervention will be collected as daily question on an electronic patient handheld device and reminders to take the study drug are planned to be sent via the device.

Further information about the participant's treatment compliance can be derived from drug concentration measurements.

6.6 **Dose Modification**

Dose modifications (dose and frequency of intake) of zabedosertib or placebo are not allowed during the intervention period of the study.

6.7 Continued Access to Study Intervention after the End of the Study

Participants who complete the treatment period or who are prematurely withdrawn from the study will not have further access to study intervention, and it will be up to the investigators discretion to provide follow-up medical care for all participants who complete the study or who are prematurely withdrawn from the study or refer them for appropriate ongoing care as required.

6.8 Treatment of Overdose

In this study, an overdose is defined as an intentional or accidental administration of zabedosertib, to or by a study participant, at a dose which is higher than the dose assigned to that individual participant according to the study protocol.

In the event of an overdose, no antidote or specific treatment is recommended. The investigator should:

- Contact the Medical Monitor immediately.
- Evaluate the participant to determine, in consultation with the Medical Monitor, if possible, whether study intervention should be interrupted or whether the dose should be reduced.
- Closely monitor the participant for any AE/SAE and laboratory abnormalities.
- Overdose per se will not be reported as an AE and/or SAE unless it is associated with clinically relevant signs and/or symptoms, or an intentional overdose taken with possible suicidal and/or self-harming intent (Section 10.3). In these cases, if feasible, a plasma sample for PK analysis may be obtained, ideally as soon as possible after the overdose, with recording of date and time of sampling.
- An overdose should be treated as clinically indicated based on signs and symptoms.
- Document the quantity of the excess dose as well as the duration of the overdose in the electronic case report form (eCRF/eDiary).

Decisions regarding dose interruptions or modifications will be made by the investigator in consultation with the Medical Monitor based on the clinical evaluation of the participant.

6.9 **Prior and Concomitant Therapy**

Any medication or vaccine (including over-the-counter or prescription medicines, recreational drugs, vitamins, and/or herbal supplements) or other specific categories of interest that the participant has received within the last 30 days before randomization visit, is receiving at the time of enrollment or receives during the study must be recorded along with:

- Reason for use
- Dates of administration including start and end dates
- Dosage information including dose and frequency.

AD relevant medication (including emollients) will be recorded for 6 months before randomization visit.

Any SARS-CoV-2 vaccination prior to study entry should be recorded independent of the timeframe under prior/concomitant medication.

The sponsor should be contacted if there are any questions regarding concomitant or prior therapy.

See Section 8, Screening, Medical history and AD history for information relating to previously used medications.

6.9.1 Background Therapy with Emollients / Moisturizers

All participants must use a stable amount (i.e., approximately the same amount for each application to the whole body at least twice daily) of emollient as background therapy during the course of the study, starting at least 7 days before the randomization visit. Any type of

emollient is permitted, but participants may not initiate treatment with prescription emollients / moisturizers or emollients / moisturizers containing additives such as urea, ceramides, hyaluronic acid, heparinoid, probiotics or any other active substances during the screening period or during the study. Participants may continue using stable amounts of such emollients / moisturizers, if initiated before the screening visit. Emollients used by the participant before entering the study should be continued with the same frequency/intensity. Participants will be reminded once a week about emollient usage by the electronic hand held device.

The emollient is considered an auxiliary medicinal product in this study (not an investigational product). The maximum daily amount and frequency of application should be agreed with the investigator and be in line with the user information.

The emollient will be locally supplied/reimbursed by the sponsor during the study, including follow-up, according to the locally agreed process.

Before the use of the defined topical rescue medication, investigators should attempt to manage participant's AD symptoms with emollients / moisturizers, e.g. with an increased frequency of use. If this is not successful or advisable, topical rescue treatment can be given to participants who are experiencing unacceptable or worsening symptoms of AD at any time after randomization visit.

For further information on the use of rescue medication, see also Section 6.9.2.

6.9.2 Rescue Medication

In the event of a disease flare or AD symptoms defined as any worsening of AD to an vIGA \geq 3 requiring escalation of treatment confirmed by an investigator, which cannot be tolerated by the study participant, topical rescue medication as defined below may be used for a timeframe of several days at the discretion of the investigator. Before topical treatment for AD (= rescue medication) is initiated, the frequency of emollient use should be increased to try to control AD symptoms and efficacy assessments should be performed (see below and Section 8.1 [Unscheduled visit]).

Defined rescue medication for this study is the methylprednisolone aceponate (Advantan[®] cream). Only if Advantan cream is not available in the respective country, an alternative TCS with similar potency may be used (see WHO definition for potent corticosteroids group III, such as betamethasone, fluclorolone, desoximetasone, fluocinolone acetonide, budesonide, mometasone, beclomethasone, hydrocortisone aceponate). If TCSs are not tolerated or their use is not advisable, the topical TCIs pimecrolimus 1% (Elidel[®] cream) or tacrolimus (Protopic[®] 0.1% or 0.03% ointment) may be used.

The rescue medication is considered an auxiliary medicinal product (not an investigational product). The daily amount and frequency of application should be once daily for 1 week. If necessary, the duration of application may be extended to a maximum of 2 weeks. The use of rescue medication has to be documented in the CRF, providing information on product, dose, frequency and duration of therapy.

Topical rescue medication will be locally supplied/reimbursed by the sponsor during the study, including follow-up, according to the locally agreed process. Whenever possible, the efficacy assessments using the EASI, vIGA-AD and BSA affected by AD should be performed immediately before start of topical rescue therapy and at its end. Site visits

(scheduled or unscheduled) are therefore strongly recommended before start of rescue treatment.

If topical rescue medication is used, study intervention (zabedosertib or placebo) will be continued and study visits performed according to the SoA (see Section 1.3).

6.9.3 **Prohibited Medication and Therapies**

Prior and concomitant therapies not permitted in this study are listed in Section 5.2, exclusion criteria. Therapies listed in the exclusion criteria are also prohibited during the study (exception: TCSs and TCIs may only be used as rescue medication).

In addition, the use of antihistamines and live vaccination are not allowed during the study.

If the participant took a prohibited medication or used a prohibited non-drug therapy for any reason, the investigator should consult with the sponsor to determine if the participant should be withdrawn from study intervention and/or the study.

For the purpose of efficacy analysis, participants receiving any pharmacologically active nonstudy medication or phototherapy for AD will be considered as treatment failures after the start of such medication, except for the use of defined topical rescue medication up to/including Week 8. Whenever possible, efficacy and safety assessments according to Visit 7 (EOT) should be conducted immediately before administering any systemic medications for AD or initiation of phototherapy (= SoC). For zabedosertib, a wash-out period of 7 days (approximately 5 half-lives) is recommended, because there is no experience or data with a combination of zabedosertib and systemic AD treatment.

SoC should be reserved for participants who do not respond adequately to topical treatment (at least 7 days of use). If a participant receives SoC treatment with systemic corticosteroids or non-steroidal systemic immunosuppressive drugs (cyclosporine, methotrexate, MMF, azathioprine, baricitinib etc.) dupilumab, tralokinumab or initiation of phototherapy, study intervention has to be discontinued and EOT assessments including FU visits performed.

7 Discontinuation of Study Intervention and Participant Discontinuation/Withdrawal

Discontinuation of specific sites or of the study as a whole are detailed in Appendix 1 (Section 10.1.11).

7.1 Discontinuation of Study Intervention

In rare instances, it may be necessary for a participant to permanently discontinue study intervention. If study intervention is permanently discontinued, the participant should, if at all possible, remain in the study to be evaluated for EOT and FU assessments, as described at the end of this section. See the SoA (see Section 1.3) for data to be collected at the time of discontinuation of study intervention and FU and for any further evaluations that need to be completed.

If an exclusion criterion is met during the study, the investigator should consider discontinuation of the participant's study intervention, if medically indicated.

The participant's study intervention must be permanently discontinued, if anything of the following occurs:

- Pregnancy (see also Section 8.4.5).
- Participant receives SoC treatment with systemic corticosteroids or non-steroidal systemic immunosuppressive drugs or phototherapy (see also Section 6.9.3).
- Participant interrupts study intervention for more than 10 consecutive days (see also Section 7.1.4).
- Participant experiences an AE which is considered to be related to study treatment or study procedure and, in the investigator's judgment, is severe enough in nature to warrant treatment discontinuation. Common Terminology Criteria for AEs (CTCAE) current version, Grade 3 or higher (may be used as guidance).
- Any malignancy.
- Febrile illness for more than 48 hours and clinical or biochemical signs of infection (e.g., clinically relevant abnormality of hsCRP level).
- Participants who received COVID-19 vaccine during the study treatment phase, must be withdrawn from the study. An interval of at least 14 days between the last study drug and the vaccine dose is recommended.
- Positive SARS-CoV-2 viral RNA test or clinical evidence for COVID-19 during the study despite a negative test result (study intervention should be interrupted until test results are available). Testing during the study should be done on an individual basis as medically indicated according to local practice, triggered by signs and symptoms of a potential SARS-CoV-2 infection or contact history. If current COVID-19 infection is confirmed, the participant must be permanently discontinued from study intervention.
- The participant's randomized treatment assignment is unblinded by the investigator or treating physician.
- Sponsor request (after discussion with the investigator), for reasons such as a significant protocol deviation or participant non-compliance.
- Study as whole is terminated by the sponsor.
- Liver safety-related discontinuation criteria are met as described in Section 7.1.1.
- Confirmed creatine kinase (CK) > 10 x ULN or clinical signs of rhabdomyolysis (Section 10.2.1).
- Herpes zoster

A participant should also be permanently discontinued from study intervention for the following **laboratory abnormalities**:

- WBC count < 1000 cells/ μ L; < 1.0 x 10⁹/L
- Absolute neutrophil count < 500 cells/ μ L; $< 0.5 \times 10^9$ /L
- Lymphocyte count < 200 cells/ μ L; < 0.2 x 10⁹/L
- Hemoglobin < 8 g/dL.

Handling of discontinuation of study intervention

For participants who permanently discontinue the study intervention, an EOT visit with all assessments as specified in the SoA (see Section 1.3) should be performed as soon as the study intervention has been discontinued. If the decision to stop the study intervention early is

taken during a site visit, this visit becomes the EOT visit. The FU visit should be performed as planned after the last dose.

After the early EOT visit, treatment with SoC may be started at the discretion of the investigator and entered into the eCRF. For zabedosertib, a wash-out period of 7 days (approximately 5 half-lives) is recommended, because there is no experience or data with a combination of zabedosertib and systemic AD treatment.

See the SoA (Section 1.3) for data to be collected at the EOT and FU and for any further evaluations that need to be completed.

7.1.1 Liver Chemistry Stopping Criteria

Permanent discontinuation of study intervention for abnormal liver tests is required by the investigator when a participant meets one of the conditions outlined below or in the presence of abnormal liver chemistry not meeting protocol-specified stopping rules if the investigator believes that it is in best interest of the participant:

- ALT or AST > 3 x ULN and total bilirubin (TBL) > 2 x ULN
- ALT or AST > 3 x ULN and INR > 1.5 x ULN ^a
- ALT or $AST > 3 \times ULN$ with appearance of fatigue, nausea, vomiting, right upper abdominal quadrant pain or tenderness, fever, rash and/or eosinophilia (> 5%)
- ALT or $AST > 5 \times ULN$ for more than 2 weeks
- ALT or $AST > 8 \times ULN$

^a Relevant only if the participant is not on Vitamin K antagonist, new oral anticoagulants (NOACs) or heparin.

• Study intervention restart or rechallenge after liver chemistry stopping criteria are met by any participant in this study is not allowed.

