At selected study sites in a subset of participants, skin biopsy samples will be taken for the assessment of gene expression and immunohistochemistry as indicated in the SoA.

Number of Participants:

Approximately 72 participants will be randomly assigned to the study to obtain 57 evaluable participants overall (2:1 randomization zabedosertib versus placebo).

Study Arms and Duration:

The total study duration per participant will be 17 to 20 weeks (approximately 140 days), with 8 study visits at intervals of 8 to 28 days with 2 study arms:

Zabedosertib at a dose of 120 mg BID orally:	48 randomized participants
Matching placebo BID orally:	24 randomized participants.

Dose changes and/or adjustments are not planned. Decisions regarding dose interruptions will be made by the investigator in consultation with the Medical Monitor based on the clinical evaluation of the participant.

Data Monitoring/Other Committee: No

Page: 13 of 93

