8.4.8 Adverse Events of Special Interest

Adverse events of special interest (AESIs) will include:

- Confirmed or suspected severe invasive bacterial infections
- Systemic hypersensitivity reactions
- Non-invasive infections (skin)
- Unexplained cases of rhabdomyolysis

AESIs must be reported in an expedited fashion as described for SAEs in Section 10.3.4.

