Other tests	randomization (if screening is not available) and EOT:	g Total immunoglobulin E (IgE)
	At screening and EOT:	Estimated glomerular filtration rate (eGFR; MDRD formula)
	Only at screening:	Hepatitis B: Hepatitis B surface antigen (HBsAg), Anti-Hepatitis B core antibody (HBcAb), Hepatitis B surface antibody
		(HBSAD) Henatitis C: (Hen C antibody)
		Human immunodeficiency virus (HIV) 1 and 2
		Tuberculosis test (QuantiFERON GOLD Plus test)
	At visit 2 and if clinically	SARS-CoV-2 RNA test (real time-PCR, test specimen
	indicated:	according to test recommendation)

For footnotes, see next page.

Footnotes to Table 10–1

¹ Details of liver chemistry stopping criteria and required actions and follow-up assessments after liver stopping or monitoring event are given in Section 7. All events of ALT \ge 3 × upper limit of normal (ULN) and bilirubin \ge 2 × ULN (> 35% direct bilirubin) or ALT \ge 3 × ULN and international normalized ratio (INR) > 1.5, if INR measured which may indicate severe liver injury (possible Hy's Law), must be reported as an SAE (excluding studies of hepatic impairment or cirrhosis).

² Lab follow up includes:

- Serum: CK (incl. isoforms), creatinine, urea nitrogen, uric acid and calcium, potassium, phosphate, Prothrombin time (PT)

Urine: urinalysis incl. myoglobin and sediment.

³ Local urine testing (pregnancy test and dipstick urinalysis) will be standard for the protocol unless serum testing is indicated by the SoA or required by local regulation or IRB/IEC.

⁴ If the participant arrives in a non-fasting state, the blood sample should be obtained and indicated in the CRF as non-fasting.

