10.3.2 Definition of SAE

An SAE is defined as any untoward medical occurrence that, at any dose, meets the one or more of the criteria listed:

a. Results in death

b. Is life threatening

• The term *life threatening* in the definition of *serious* refers to an event in which the participant was at risk of death at the time of the event. It does not refer to an event, which hypothetically might have caused death, if it were more severe.

c. Requires inpatient hospitalization or prolongation of existing hospitalization

- In general, hospitalization signifies that the participant has been admitted (usually involving at least an overnight stay) at the hospital or emergency ward for observation and/or treatment that would not have been appropriate in the physician's office or outpatient setting. Complications that occur during hospitalization are AEs. If a complication prolongs hospitalization or fulfills any other serious criteria, the event is serious. When in doubt as to whether hospitalization occurred or was necessary, the AE should be considered serious.
- Hospitalization for elective treatment of a pre-existing condition that did not worsen from baseline is not considered an AE.

d. Results in persistent or significant disability/incapacity

- The term disability means a substantial disruption of a person's ability to conduct normal life functions.
- This definition is not intended to include experiences of relatively minor medical significance such as uncomplicated headache, nausea, vomiting, diarrhea, influenza, and accidental trauma (e.g., sprained ankle) that may interfere with or prevent everyday life functions but do not constitute a substantial disruption.

e. Is a congenital anomaly/birth defect

f. Other situations:

- Medical or scientific judgment should be exercised by the investigator in deciding whether SAE reporting is appropriate in other situations such as significant medical events that that may not be immediately life-threatening or result in death or hospitalization but may jeopardize the participant or may require medical or surgical intervention to prevent one of the other outcomes listed in the above definition. These events should usually be considered serious.
 - Examples of such events include invasive or malignant cancers, intensive treatment in an emergency room or at home for allergic bronchospasm, blood dyscrasias, convulsions, or development of intervention dependency or intervention abuse.

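### Possible Hy's Law is a mandatory SAE on ALT alone, while the linked stopping criteria and the SAP's definition use ALT or AST

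*Protocol*

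**What the plan says.** Protocol 7.1.1 lists the liver findings that require permanent discontinuation. Every criterion is written for either transaminase. The two that matter here are "ALT or AST > 3 x ULN and total bilirubin (TBL) > 2 x ULN" and "ALT or AST > 3 x ULN and INR > 1.5 x ULN", the second not applied to participants on anticoagulants. Once a criterion is met, "Study intervention restart or rechallenge after liver chemistry stopping criteria are met by any participant in this study is not allowed".

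Footnote 1 to Table 10-1 (Protocol 10.2) points to Section 7 for the stopping criteria and then sets a reporting rule for possible Hy's Law. It has two limbs. One is ALT of at least 3 x ULN with bilirubin of at least 2 x ULN, more than 35% of it direct. The other is ALT of at least 3 x ULN with "international normalized ratio (INR) > 1.5, if INR measured which may indicate severe liver injury". Events meeting either limb "must be reported as an SAE (excluding studies of hepatic impairment or cirrhosis"). AST appears in neither limb.

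SAP 4.5.3 defines a potential Hy's Law case for its screening plot on ALT or AST. Its table of liver abnormalities repeats the 7.1.1 criteria, again with either transaminase.

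Protocol 8.4.1 requires SAEs to reach the sponsor within 24 hours. Protocol 8.4.8 says that "AESIs must be reported in an expedited fashion as described for SAEs in Section 10.3.4", but its four categories are severe invasive bacterial infection, systemic hypersensitivity, non-invasive skin infection and unexplained rhabdomyolysis. None is a liver event.

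**The concern.** The stopping rule and the reporting rule address the same clinical signal, and the footnote links them. They disagree on which enzyme counts. A case driven by AST is serious enough to end treatment permanently and bar rechallenge, but it is not automatically an SAE.

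What is at stake is the speed and certainty of reporting. The participant has already stopped. A clinically significant laboratory change is recorded as an AE (8.3.4), an AE that led to discontinuation is followed up (8.4), and TEAEs leading to discontinuation are listed separately (9.3.3.1). What is missing is the obligation to report within 24 hours. Unless another seriousness criterion such as hospitalization applies, that depends on 10.3.2 f, where "Medical or scientific judgment should be exercised by the investigator in deciding whether SAE reporting is appropriate in other situations". Protocol 4.4 notes that there is no earlier clinical experience with the drug in atopic dermatitis, so a liver signal should not depend on how one site reads the case.

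**Working it through.** No sample size, power or event-rate figure enters here. The check sets the rules side by side and applies them to worked cases.

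| Element | Protocol 7.1.1 (stop) | Table 10-1, footnote 1 (SAE) | SAP 4.5.3 (plot) |
|---|---|---|---|
| Transaminase | ALT or AST, > 3 x ULN | ALT only, >= 3 x ULN | ALT or AST, >= 3 x ULN |
| Bilirubin | > 2 x ULN | >= 2 x ULN and > 35% direct | >= 2 x ULN within 30 days after the transaminase rise |
| INR | > 1.5 x ULN, no anticoagulant | > 1.5, if measured | not used |
| ALP | not used | not used | maximum < 2 x ULN |

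On the transaminase, the footnote is the one that differs. The >= versus > difference matters only at exact boundary values and is not part of this point.

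**Inputs.** SAP Table 8-4 gives the same ULN for AST and ALT: 50 U/L in men and 35 U/L in women. So 3 x ULN is 3 x 50 = 150 and 3 x 35 = 105 U/L, and 4 x ULN is 200 and 140 U/L.

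**Case A, bilirubin limb.** A man has AST 200 U/L (200/50 = 4.0 x ULN), ALT 120 U/L (120/50 = 2.4 x ULN), bilirubin 2.5 x ULN and 40% direct.
- 7.1.1: AST is above 3 x ULN and bilirubin above 2 x ULN, so he must stop permanently.
- SAP plot: he is marked as a potential Hy's Law case if the 30-day and ALP conditions are met.
- Footnote 1: ALT is below 3 x ULN, so there is no mandatory SAE.
- With AST added to the footnote: mandatory SAE.

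**Case B, INR limb.** AST 4 x ULN, ALT 1 x ULN, INR 2.1, no anticoagulant. The documents give no ULN for INR. For an assumed ULN of 1.0, 1.1, 1.2 or 1.3, the 7.1.1 limit is 1.5 x ULN = 1.50, 1.65, 1.80 or 1.95. An INR of 2.1 exceeds all four, so the stop applies throughout. Footnote 1 is again not met because ALT is normal. With AST added, it is met.

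**Secondary note, Case C.** ALT 4 x ULN, INR 1.6, no anticoagulant, nothing else abnormal. Footnote 1 makes this a mandatory SAE. The 7.1.1 INR criterion is met at an assumed ULN of 1.0 (1.6 > 1.50) but not at 1.1, 1.2 or 1.3. The window between the two limits is 0, 0.15, 0.30 or 0.45. This mismatch runs the other way: the reporting rule is wider than the stopping rule.

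**The case against.** Four arguments can be made against the point.

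First, the sponsor would probably hear of an AST-driven case anyway. Protocol 8.1 asks that immediate safety concerns be discussed with the sponsor at once, and 10.3.2 f says that medically important events should usually be considered serious. This stands in part. A reader might infer that such a case could leave the sponsor uninformed, and the documents do not support that. Nor does the entry "Data Monitoring/Other Committee: No" in the Synopsis strengthen the concern, since such a committee is not the protocol's channel for individual case reports. But both routes depend on the site recognising the case, and neither imposes the 24-hour SAE report.

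Second, an ALT-only rule may be sensible where muscle injury is a named risk, because AST also rises from muscle. This has limited force. An isolated AST rise would still not qualify. The bilirubin limb would also need bilirubin of at least 2 x ULN with more than 35% direct, and the other limb an INR above 1.5.

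Third, the SAP definition serves a display and need not match a reporting rule. That is fair, but the mismatch with 7.1.1 remains without it.

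Fourth, adding AST does not make the two rules identical. A case with 30% direct bilirubin would still stop without a mandatory SAE. That is true, but the direct-bilirubin condition has a plausible purpose, since exclusion criterion 22 allows Gilbert's syndrome. Keeping it is a choice; no such reason is given for omitting AST.

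A reader might also infer from Case C that the protocol labels an event possible Hy's Law and then permits re-dosing, and treat the INR difference as an error of equal weight. The documents do not support this. It needs an INR ULN above 1.0, which they do not give, and a reporting trigger wider than the stopping trigger is cautious. The opening sentence of 7.1.1 requires a stop for abnormal liver chemistry short of the listed limits when the investigator judges it best for the participant. Decisions on dose interruption are taken with the Medical Monitor (Synopsis).

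**Conclusion.** The point holds for the transaminase. An AST-driven case with bilirubin above 2 x ULN and more than 35% direct must stop permanently, but no stated rule makes it an SAE and no AESI category catches it. The same gap exists in the INR limb. This follows from the text and, for the bilirubin limb, needs no assumption.

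The size is minor. The documents give no event rate, but few such cases are likely in 72 participants. Judgement-based routes soften the gap, and no efficacy analysis is affected. The INR difference is a wording note only: it has an effect only if the laboratory's INR ULN exceeds 1.0, and which limit to adopt is the sponsor's choice.

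**What to change.** Name ALT or AST in both limbs of footnote 1 to Table 10-1. The direct-bilirubin condition can stay. If the footnote is opened for this, the sponsor could also choose one INR limit for the footnote, 7.1.1 and the matching SAP 4.5.3 row, but that is optional.

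The cost is a protocol amendment to one footnote, with ethics and authority approval if judged substantial, and possibly a few more SAE reports. Some may be AST rises of muscle origin; CK in the same safety panel helps to identify these. Sample size and efficacy analyses do not change.

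The benefit depends on timing. SAP 4.7 puts about 90% of participants as randomized by 02-AUG-2023; Day 84 for a participant starting that day is 83 days later, 24-OCT-2023. A change at the SAP date of 31 OCT 2023 could therefore reach at most about 10% x 72 = 7 participants on treatment. The main gain is from correcting the wording earlier, or before it is carried into later studies of the compound.
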